10.3.3. Reporting Standards for Pharmacokinetics

Pharmacokinetic Con	centration Data
Pharmacokinetic Con Descriptive Summary Statistics, Graphical Displays and Listings	Refer to IDSL PK Display Standards. Refer to IDSL Statistical Principle 6.06.1. For continuous data: NQs at the beginning of a participant profile (i.e. before the first incidence of a measurable concentration) are deemed to be zero as it is assumed that in this circumstance no drug is yet measurable in the blood. For NQs at the end of the participant profile (i.e. after the last incidence of a measurable concentration); for individual plots and pharmacokinetic analyses these are dropped (set to missing) as they do not provide any useful information (and can erroneously indicate that absolutely no drug is present) for summary statistics, these are set to 0 (to avoid skewing of the summary statistics) Individual NQs which fall between two measurable concentrations are set to missing (individual values of this nature are assumed to be an anomaly) If two or more NQ values occur in succession between measurable concentrations, the profile will be deemed to have terminated at the last measurable concentration prior to these NQs. For the purpose of individual participant plots, these NQs will be set to 0, and the subsequent measurable concentrations will be retained. For the derivation of pharmacokinetic parameters, these NQs and any subsequent
	measurable concentrations will be omitted (set to missing). Note: Concentration values will be imputed as per GUI_51487 for descriptive
	summary statistics/analysis and summarized graphical displays only.
Pharmacokinetic Para	
Descriptive Summary Statistics, Graphical Displays and Listings	N, n, geometric mean, 95% CI of geometric mean, SD of logged data and between-subject geometric coefficient of variation (CVb (%)) will be reported. $ \text{CV}_{\text{b}} \left(\%\right) = \sqrt{\left(\text{exp}(\text{SD}^2) - 1\right) * 100} $ (SD = SD of Ln-Transformed data)
Parameters Not Being Ln- Transformed	Tmax, λz, λz lower, λz upper, and λz no. of points.
Parameters Not Being Summarized	λz, λz lower, λz upper, and λz no. of points.
Listings	Include the first point, last point and number of points used in the determination of λz and Rsq_adjusted for listings.

10.4. Appendix 4: Derived and Transformed Data

10.4.1. General

Multiple Measurements at One Analysis Time Point

- Mean of the measurements will be calculated and used in any derivation of summary statistics but if listed, all data will be presented.
- The worst finding/interpretation associated with multiple measurements as the finding/interpretation for that time point.
- Participants having both High and Low values for Normal Ranges at any post-baseline visit for safety parameters will be counted in both the High and Low categories of "Any visit post-baseline" row of related summary tables. This will also be applicable to relevant Potential Clinical Importance summary tables.

Study Day

- Calculated as the number of days from First Dose Date in Period 1:
 - Ref Date = Missing
- → Study Day = Missing
- Ref Date < First Dose Date in Period 1 → Study Day = Ref Date First Dose Date
- Ref Date >= First Dose Date in Period 1 → Study Day = Ref Date (First Dose Date in Period 1) +

Period Day

- Calculated as the number of days from First Dose Date for the respective period:
 - Ref Date = Missing
- → Study Day = Missing
- Ref Date < First Dose Date in Period 1 → Study Day = Ref Date First Dose Date
- First Dose Date in Period 1 <= Ref Date < First Dose Date in Period 2 → Study Day = Ref Date –
 (First Dose Date in Period 1) + 1
- First Dose Date in Period 2 <= Ref Date < First Dose Date in Period 3 → Study Day = Ref Date –
 (First Dose Date in Period 2) + 1
- Ref Date >= First Dose Date in Period 3 → Study Day = Ref Date (First Dose Date in Period 3) +

10.4.2. Study Population

Age

- GSK standard IDSL algorithms will be used for calculating age where birth date will be imputed as follows:
 - Any participant with a missing day will have this imputed as day '15'.
 - Any participant with a missing day and month will have this imputed as '30th June'.
- Birth date will be presented in listings as 'YYYY'.

Body Mass Index (BMI)

Calculated as Weight (kg) / [Height (m)²]

10.4.3. Safety

Adverse Events

AEs of Special Interest

No analysis for AEs of Special Interest will be performed

10.5. Appendix 5: Reporting Standards for Missing Data

10.5.1. Premature Withdrawals

Element	Reporting Detail
General	 Participant study completion (i.e. as specified in the protocol) was defined as the participant has completed all phases of the study including the final date on which data were or are expected to be collected. Withdrawn participants were not replaced in the study. All available data from participants who were withdrawn from the study will be listed and all available planned data will be included in summary tables and figures, unless otherwise specified.

10.5.2. Handling of Missing Data

Element	Reporting Detail
General	Missing data occurs when any requested data is not provided, leading to blank fields on the collection instrument:
	 These data will be indicated by the use of a "blank" in participant listing displays. Unless all data for a specific visit are missing in which case the data is excluded from the table.
	 Answers such as "Not applicable" and "Not evaluable" are not considered to be missing data and should be displayed as such.
Outliers	Any participants excluded from the summaries and/or statistical analyses will be documented along with the reason for exclusion in the clinical study report.

10.5.2.1. Handling of Missing and Partial Dates

Element	Reporting Detail		
General	Partial dates will be displayed as captured in participant listing displays.		
Adverse Events	 The eCRF allows for the possibility of partial dates (i.e., only month and year) to be recorded for AE start and end dates; that is, the day of the month may be missing. In such a case, the following conventions will be applied for calculating the time to onset and the duration of the event: Missing Start Day: First of the month will be used unless this is before the start date of study treatment; in this case the study treatment start date will be used and hence the event is considered On-treatment as per Appendix 4: Study Phases and Treatment Emergent Adverse Events. Missing Stop Day: Last day of the month will be used, unless this is after the stop date of study treatment; in this case the study treatment stop date will be used. Completely missing start or end dates will remain missing, with no imputation applied. Consequently, time to onset and duration of such events will be missing. 		
Concomitant Medications	 Partial dates for any concomitant medications recorded in the eCRF will be imputed using the following convention: If the partial date is a start date, a '01' will be used for the day and 'Jan' will be used for the month If the partial date is a stop date, a '28/29/30/31' will be used for the day (dependent on the month and year) and 'Dec' will be used for the month. The recorded partial date will be displayed in listings. 		

10.6. Appendix 6: Division of AIDS (DAIDS) Table for Grading the Severity of Adult and Pediatric Adverse Events

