8.3.1. Time Period and Frequency for Collecting AE and SAE Information

- All SAEs will be collected from the signing of the ICF until the end of the study at the time points specified in the SoA (Section 1.3).
- All AEs will be collected from the start of intervention until the end of the study at the time points specified in the SoA (Section 1.3).
- Medical occurrences that begin before the start of study intervention but after obtaining informed consent will be recorded on the Medical History/Current Medical Conditions section of the CRF, not the AE section.
- All SAEs will be recorded and reported to the sponsor or designee immediately and under no circumstance should this exceed 24 hours, as indicated in [Appendix 6](#). The investigator will submit any updated SAE data to the sponsor within 24 hours of it being available.
- Investigators are not obligated to actively seek AEs or SAEs after the conclusion of the study participation. However, if the investigator learns of any SAE, including a death, at any time after a participant has been discharged from the study, and he/she considers the event to be reasonably related to the study intervention or study participation, the investigator must promptly notify the sponsor.

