5. CONSIDERATIONS FOR DATA ANALYSES AND DATA HANDLING CONVENTIONS

5.1. Study Treatment & Sub-group Display Descriptors

Treatment Group Descriptions				
Data Displays for Reporting				
Description	Code	Order in TLF		
DTG 50 mg QD on Days 1 through 5 in Period 1	DTG 50 mg	1		
GSK3640254 200 mg QD on Days 1 through 7 in Period 2	GSK3640254 200 mg	2		
DTG 50 mg QD + GSK3640254 200 mg QD on Days 1 through 7 in Period 3	DTG 50 mg + GSK3640254 200 mg	3		

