10.2.2. Treatment Emergent Flag for Adverse Events

Flag	Definition
Treatment Emergent	 If AE onset date and time is on or after treatment start date and time & on or before treatment stop date and time + 5 days. Study Treatment Start Date and Time ≤ AE Start Date and Time ≤ Study Treatment Stop Date and Time + 5 days. If the AE onset date is completely missing, the AE is considered as treatment emergent.

NOTES:

- If the study treatment stop date is missing, then the AE will be considered to be On-Treatment.
- Please refer to Appendix 5: Reporting Standards for Missing Data for handling of missing and partial dates for adverse events. Use the rules in this table if the adverse event onset date is completely missing.

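### The missing-onset-day rule for adverse events ignores treatment period, stop date and a pre-dose recorded month, so in this fixed-sequence trial it can only date on-study onsets too early and leaves treatment assignment undefined

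*SAP*

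**What the plan says.** SAP 10.5.2.1 covers adverse events whose onset month and year are recorded without the day. The rule begins "First of the month will be used unless this is before the start date of study treatment; in this case the study treatment start date", and the consequence of that floor is stated: "in this case the study treatment start date will be used and hence the event is considered On-treatment". The stated purpose is narrow: "the following conventions will be applied for calculating the time to onset and the duration of the event". The treatment-emergent flag in SAP 10.2.2 nevertheless relies on the same appendix: "Please refer to Appendix 5: Reporting Standards for Missing Data for handling of missing and partial dates for adverse events".

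SAP 10.2.1 and 10.2.2 use one study-level treatment start date. Where the SAP means period-level first-dose dates, as for Period Day in 10.4.1, it names them. SAP 5.1 defines three display groups in a fixed order, the last being "DTG 50 mg QD + GSK3640254 200 mg QD on Days 1 through 7 in Period 3". SAP 10.3.2 reports data by the treatment actually received. No section says how an adverse event with a partial onset date is assigned to one of the three groups.

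On collection, Protocol 8.3.1 states: "All SAEs will be collected from the signing of the ICF until the end of the study". Non-serious events are collected only from the start of intervention; earlier occurrences go to medical history.

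**The concern.** Taking the earliest possible date is a reasonable convention in a parallel-group trial: it keeps a doubtful event on treatment, and the participant has only one treatment. Here the earliest possible date also tends to be the earliest treatment, which is DTG alone for everyone. If the imputed date drives the by-treatment tables, events that began on GSK3640254 or the combination would be credited to an earlier treatment and never to a later one. Safety of each drug alone and together is a secondary objective, and the planned group is about 16 participants, so one reassigned event changes an incidence by 1/16, about 6 percentage points.

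A second problem does not depend on treatment assignment. The start-date floor has no lower check. An SAE recorded in a month that ended before dosing is still moved to the first dose and called On-treatment, against its own recorded month.

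**Working it through.** **Calendar.** Protocol 4.1 gives screening of up to 28 days, DTG on Days 1 to 5, a 4-day washout, GSK3640254 for 7 days, and Period 3 with discharge on Day 11. The sum is 28 + 5 + 4 + 7 + 11 = 55 days, which matches the protocol's approximate study duration. In study days, DTG alone with washout is 1–9, GSK3640254 alone 10–16, and combination with follow-up 17–27.

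**Rule.** Imputed onset = max(first of the recorded month, first dose date).

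**Example.** With first dose on 4 March, Period 2 starts on 13 March, Period 3 on 20 March, and discharge is on 30 March. Any event dated only to March receives 4 March, under DTG alone, even if it began on the combination.

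**Enumeration.** The plan gives no figure for this rule. Assumptions: first dose equally likely on each of 365 dates, true onset uniform over study days 1–27, washout counted with DTG alone, and the imputed date used to choose the treatment. This gives 365 × 27 = 9,855 combinations.

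| True onset | Combinations | Dated to DTG alone | Dated to GSK3640254 alone | Dated to combination |
|---|---|---|---|---|
| DTG alone (days 1–9) | 3,285 | 3,285 (100%) | 0 | 0 |
| GSK3640254 alone (10–16) | 2,555 | 2,219 (86.8%) | 336 (13.2%) | 0 |
| Combination (17–27) | 4,015 | 2,299 (57.3%) | 924 (23.0%) | 792 (19.7%) |

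- Periods 2 and 3 pooled (2,555 + 4,015 = 6,570): (2,219 + 2,299)/6,570 = 68.8% go to DTG alone; 924/6,570 = 14.1% move from combination to GSK3640254 alone; (336 + 792)/6,570 = 17.2% stay.
- All onsets: (2,219 + 2,299 + 924)/9,855 = 55.2% land in the wrong period, ranging from 25.9% to 66.7% by first-dose date.
- DTG alone receives (3,285 + 2,219 + 2,299)/9,855 = 79.2%, against a true share of 9/27 = 33.3%.
- Onset error (true day minus imputed day): mean 9.0 days, maximum 26 (day 27 dated to day 1), never negative.

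**Sensitivity.** By month length (28, 30 or 31 days), the pooled share going to DTG alone is 66% to 69%. Restricting combination onsets to dosing days 17–23 raises it to about 75%. The start date matters more. In a 30-day month, most Period 2–3 onsets go to DTG alone when first dose falls on days 1–12 or 23–30 (20 of 30). When it falls on days 16–22, every combination onset goes to GSK3640254 alone.

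**Pre-dose SAE.** Take first dose on 20 February and an SAE dated only to January. Screening may begin 28 days earlier, on 23 January, so this is possible. The first of January precedes first dose, so the rule gives 20 February and On-treatment. If the event stopped on 5 February, imputed onset falls 15 days after the stop.

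**The case against.** The best defence is that the rule is written for time to onset and duration, and that the treatment-emergent flag it also feeds compares dates with study-level start and stop, not with periods. On that flag the rule is harmless for on-study events. No text says that the imputed date picks the treatment column, adverse event displays follow sponsor standards that are not in the documents, and no planned display is titled as a time-to-onset analysis. This stands: misattribution in the by-treatment tables is an inference. It is a fair one, because the SAP defines no other onset date for these events.

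The affected number is also likely to be very small. Participants live in the clinic from Day −1 to Period 3 Day 11, and dosing is supervised and timed. That the eCRF allows a missing day does not show that missing days will occur. The percentages above apply only within a group whose size the documents do not give. The pre-dose SAE case is rarer still. It needs a serious event in a healthy volunteer who is still dosed.

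Listings show partial dates as captured, so the missing day remains visible there. That does not correct a summary table.

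One counter-reading fails: taking the start date as that of the current period is circular when the onset day, and hence the period, is unknown.

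**Conclusion.** The point holds as a minor defect in a stated rule. For any day-missing on-study event the imputed onset is on or before the true one, and the rule discards recorded information that could correct it. The mean error of 9 days and the pooled shares of about 69% and 14% rest on uniform onsets and evenly spread first-dose dates; the two shares also require the imputed date to determine treatment. The pre-dose SAE error needs none of these assumptions.

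A reader might infer that the safety tables will systematically clear GSK3640254 and the combination at the expense of DTG alone. The documents do not support that. The SAP has no explicit rule assigning adverse events to treatments, and continuous confinement should leave few such events. Nor do all misplaced events go to DTG alone: about 23% of combination onsets would be added to GSK3640254 alone, and for about a third of first-dose dates (120 of 365) DTG alone does not receive a majority of Period 2–3 onsets.

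**What to change.** Replace the Missing Start Day rule in SAP 10.5.2.1 with bounds taken from recorded dates.

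- **Lower bound:** the later of the first of the recorded month and the consent date. For non-serious events, which are collected only from the start of intervention, the first dose is the effective floor.
- **Upper bound:** the earlier of the end of the recorded month and the recorded (not imputed) stop date. Add the report date if it is captured; the documents do not show that it is for non-serious events.
- **Pre-dose:** if the recorded month or the stop date precedes the first dose, classify the event as Pre-Treatment and do not move it.
- **One period:** if the bounds fall within one period, assign that treatment.
- **Several periods:** keep the event treatment-emergent, flag it as period not determinable, footnote how the counts change under earliest and latest assignment, and do not report its time to onset.

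Assigning by default to the latest treatment started would only reverse the problem. With no narrowing dates, the same enumeration puts 50% of events in the wrong period, including 84% of true DTG-alone and 87% of true GSK3640254-alone onsets.

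The cost is SAP wording and a few lines of programming. The downside is that a few events may appear outside the three treatment columns.

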7. DISCONTINUATION OF STUDY INTERVENTION AND PARTICIPANT DISCONTINUATION/WITHDRAWAL

7.1. Discontinuation of Study Intervention

In rare instances, it may be necessary for a participant to permanently discontinue study intervention. If study intervention is permanently discontinued, the participant will remain in the study to be evaluated for safety. See the SoA (Section 1.3) for data to be collected at the time of discontinuation of study intervention.

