8.3. Adverse Events and Serious Adverse Events

The definitions of an AE or SAE can be found in [Appendix 6](#). As described in [Appendix 6](#), intensity of AEs (and laboratory abnormalities) will be graded using the most recent version of the Division of AIDS (DAIDS) grading table at the time of the last subject last visit. While the study population will consist of HIV-1 seronegative healthy volunteers, the DAIDS criteria will be used in later clinical studies (Phase 2a and beyond); additionally, the DAIDS criteria have a more conservative grading scale relative to other scales (eg. CTCAE v 4.0). Thus, participant safety evaluation and monitoring will be more conservative.

The investigator and any qualified designees are responsible for detecting, documenting, and reporting events that meet the definition of an AE or SAE, and remain responsible for

following up AEs that are serious, considered related to the study intervention or the study, or that caused the participant to discontinue the study (see Section 7).

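### The SAP's rule for a missing adverse event stop day has no check against onset or the recorded stop month, so events starting after the last dose get an imputed end before they began

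*SAP*

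**What the plan says.** SAP section 10.5.2.1 covers adverse event dates with month and year recorded but the day missing. It states their purpose: "the following conventions will be applied for calculating the time to onset and the duration of the event". For a missing stop day the rule is "Last day of the month will be used, unless this is after the stop date of study treatment"; and, if it is, "in this case the study treatment stop date will be used". No floor at onset is given there, and none was found elsewhere in the SAP. The section also says of listings: "Partial dates will be displayed as captured in participant listing displays".

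The plan expects events after the last dose. Protocol section 8.3.1 says "All AEs will be collected from the start of intervention until the end of the study". SAP section 10.2.2 flags an event as treatment emergent when "Study Treatment Start Date and Time ≤ AE Start Date and Time ≤ Study Treatment Stop Date and Time + 5 days". Protocol section 4.1 puts the last dose on Period 3 Day 7 and discharge on Period 3 Day 11.

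For a participant who stops treatment early, Protocol section 7.1 says "the participant will remain in the study to be evaluated for safety". Protocol section 8.3 gives the investigator the duty of "following up AEs that are serious, considered related to the study intervention or the study, or that caused the participant to discontinue the study".

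**The concern.** The cap assumes that no event outlasts treatment, while the collection window and the treatment-emergent window both run past it. Three consequences follow when the stop day is missing:

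- An event that begins after the last dose is given an end before its beginning.
- An event recorded as stopping in a later month than the last dose is given an end that contradicts the month on the case report form.
- An event that begins during dosing and outlasts it is cut off at the last dose. This also applies after early discontinuation, where the event that led to stopping would be ended on the day treatment stopped.

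At stake is the derived event duration, which would be impossible in the first case, inconsistent with the recorded month in the second and too short in the third.

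**Working it through.** The SAP states no figure to reproduce, so the check applies the rule as written.

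**Inputs.** From the treatment periods in Protocol section 4.1 and the schedule of activities: Period 1 dosing is study days 1-5, washout is days 6-9, Period 2 is days 10-16 and Period 3 dosing is days 17-23. Last dose is day 23. Discharge (Period 3 Day 11) is day 27. *Assumption:* treatment stop is the whole-study date, day 23; the SAP does not say whether it is per period.

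**Rule.** Imputed end = the earlier of the month end of the recorded stop month and day 23. If the true stop is after day 23, its month end is also after day 23. The cap therefore always applies and the imputed end is day 23.

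**Onset after the last dose.** Imputed end minus onset:

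| Onset | Study day | End − onset |
|---|---|---|
| Period 3 Day 8 | 24 | 23 − 24 = −1 |
| Day 9 | 25 | 23 − 25 = −2 |
| Day 10 | 26 | 23 − 26 = −3 |
| Day 11 | 27 | 23 − 27 = −4 |

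The SAP gives no duration formula. Counted as end − onset + 1, the durations are 0, −1, −2 and −3 days.

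**Onset by the last dose, true stop on days 24-27.** Days lost = true stop − 23 = 1, 2, 3 or 4. Example: onset day 22 and true stop day 27 give 27 − 22 = 5 days; the rule gives 23 − 22 = 1. For an event followed beyond discharge, the loss is the whole time from last dose to true stop.

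**Over the calendar.** The rule was applied to 365 first-dose dates in an illustrative year (2019) and to all onset/stop pairs on days 1-27.

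- Onset on days 24-27: 4 + 3 + 2 + 1 = 10 pairs × 365 = 3650 combinations. The imputed end precedes onset in all 3650.
- Onset on days 1-23, stop on days 24-27: 23 × 4 × 365 = 33,580 combinations. The end is too early in all 33,580.
- Of these 3650 + 33,580 = 37,230 combinations, 3120 (8.4%) put the end outside the recorded stop month.

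**Effect of a floor.** Taking the latest of the current imputed date, onset, and the first day of the recorded stop month leaves no end before onset and none outside the recorded month. It changes nothing for true stops on days 1-23.

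**Effect of also replacing the cap** with last contact (day 27), stop days weighted equally:

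| True stop | Current rule: days late | Last-contact cap: days late |
|---|---|---|
| Days 1-23 (23 × 365 = 8395) | 0 to 22, mean 8.1 | 0 to 26, mean 10.3 |
| Days 24-27 | 1 to 4 days early | 0 to 3 |

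For stops on days 1-23 the last-contact cap is further from the truth in 5083 of 8395 combinations, equal in 3312 and closer in none. Over all 27 stop days the mean absolute error rises from 7.3 to 9.0 days.

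**The case against.** The strongest objection is that nothing reported is shown to change. No title among adverse event Tables 2.1-2.6 or Listings 11-17 mentions duration, listings keep partial dates as captured, and the treatment-emergent flag uses onset only. The trigger is also unlikely, because participants are confined until Period 3 Day 11 and site staff are present throughout the 4-day window. All of this stands and limits the point to a minor one. It does not rescue the rule, because the SAP says the imputed date feeds a duration. Whether the shell for Listing 13 (AE9CP) prints duration cannot be seen.

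A second objection is that shortening some events is ordinary imputation error. That also largely stands. A reader might infer that the cap should simply be replaced by last contact because this brings the imputed end within 0-3 days of the truth. The schedule does not support that inference: the 0-3 figure holds only for stops on study days 24-27, and events resolved by the last dose become more overstated.

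A reader might also see a defect in SAP section 10.2.1 using < at treatment start where 10.2.2 uses ≤. For adverse events, 10.2.2 and 10.5.2.1 already settle that case. Changing the On-Treatment bound to ≤ would overlap with the Pre-Treatment bound, which is already ≤. No change is warranted there.

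**Conclusion.** The rule in SAP section 10.5.2.1 is wrong as written, and the point is minor. With a missing stop day, onset on Period 3 Days 8-11 always yields an end 1-4 days before onset, and a recorded stop month later than that of the last dose always yields an end outside that month. Events that start during dosing and truly end on Days 8-11 lose 1-4 days; this is a matter of imputation accuracy, not an impossibility.

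The figures rest on the whole-study reading of treatment stop. Under a per-period reading, events with onset in the washout (Period 1 Days 6-9, after last dose on Day 5) could meet the same problem. The documents do not give the number of missing stop days.

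A reader might infer that the safety results are compromised. The documents do not support that: event counts, the treatment-emergent flag and the PK analyses do not use the imputed stop date.

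**What to change.** In SAP section 10.5.2.1, add that an imputed stop date may never be earlier than the onset date (recorded or imputed) or the first day of the recorded stop month. This costs one sentence and one line of derivation, with no new data.

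Optional: replace the treatment-stop cap with the participant's last contact date. This removes the truncation of events that outlast dosing, at the price of more overstatement for events that ended by the last dose. If adopted, the SAP should state that trade-off. The two floors should be kept either way.

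Editorial: 10.5.2.1 cites Appendix 4 for the study phases; they are in Appendix 2.
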